3.1.3.4. Adverse Events

Standard algorithms for handling missing AE dates and missing AE severity will be applied as described in the Pfizer Vaccine data standard rules.

The following derivations will be included for each participant:

1. Any AE reported
2. Any related AE reported
3. Any immediate AE (AE start time is within 30 minutes after vaccination)
4. Any severe AE
5. Any life-threatening AE
6. Any AE leading to study withdrawal

Each of the above will be derived for the following analysis intervals:

1. Within 1 month after Vaccination 1 (AEs starting after Vaccination 1 through Visit 2 [before Vaccination 2]).
2. Within 1 month after Vaccination 2 (AEs starting after Vaccination 2 through Visit 3 [inclusive]).

AEs starting after RSVpreF vaccination throughout the study may also be derived.

3.1.3.5. Serious Adverse Events

SAEs are collected throughout the study. The following SAE-related variables will be derived:

1. SAEs within 1 month after Vaccination 1.
2. SAEs within 1 month after Vaccination 2.

SAEs starting after RSVpreF vaccination throughout the study may also be derived.

3.1.4. Secondary Immunogenicity Endpoints

3.1.4.1. RSV A– and RSV B–Neutralizing Antibody Titers

RSV A– and RSV B–neutralizing antibody titers will be determined at each visit.

Titers above the LLOQ are considered accurate and their quantitated values will be reported. Refer to [Section 5.3.2](#) for LLOQ details. Titers below the corresponding LLOQ, or denoted as BLQ, will be set to $0.5 \times \text{LLOQ}$ for analysis. Missing assay results will not be imputed.

RSV A and RSV B NTs at each blood sampling time point are included in the assay result data, thus no derivation is needed. The following variables will be derived for each participant:

1. RSV A/B at each blood sampling time point: This will be derived as the geometric mean of RSV A and RSV B NTs measured at each blood sampling time point.
2. RSV A, RSV B, and RSV A/B NT fold rise: This will be derived from before vaccination with RSVpreF to each visit after RSVpreF vaccination. The numerator is the postvaccination value and the denominator is the prevaccination value. For the coadministration group, assay results at Visit 1 will be used. For the sequential-administration group, assay results at Visit 2 will be used, if both Visit 1 and Visit 2 data are available; otherwise, the assay results at Visit 1 will be used, if only Visit 1 assay results are available.

When calculating a fold rise, if assay results are $< \text{LLOQ}$, the assay results will be converted to $0.5 \times \text{LLOQ}$, except when the prevaccination assay result is $< \text{LLOQ}$ while the postvaccination result is $\geq \text{LLOQ}$, in which case the prevaccination value will be set to LLOQ.

3.1.4.2. HAI (or H3N2-Neutralizing Antibody) Titers

HAI (or H3N2-neutralizing antibody) titers to the influenza strains in the SIIV administered will be determined on sera collected at Visits 1 and 2.

Only the fold rise on HAI (or H3N2-neutralizing antibody) titers will be derived for each influenza strain in the SIIV. Similar to NTs, when calculating a fold rise, if assay results are $< \text{LLOQ}$, the assay results will be converted to $0.5 \times \text{LLOQ}$, except when the prevaccination assay result is $< \text{LLOQ}$ while the postvaccination result is $\geq \text{LLOQ}$, in which case the prevaccination value will be set to LLOQ.

3.2. Other Endpoint(s)

3.2.1. Exploratory Endpoints

In addition to the endpoints included in [Section 3.1.1](#), [Section 3.1.2](#), and [Section 3.1.4](#), the following variables will be derived for exploratory endpoints for each participant:

CCI

3.2.1.2. HAI (or H3N2-Neutralizing Antibody) Titer Seroprotection

HAI seroprotection is defined as an HAI titer $\geq 1:40$. This will be derived for each participant at Visit 1 and Visit 2.

If a meaningful HAI is not obtainable, seroprotection for H3N2 NTs will be defined as an H3N2 NT $\geq 1:80$. Although no widely agreed cutoff protective level for NTs is available, estimates in the literature for neutralizing protective levels against H3N2 viruses range from 1:40 to 1:160. However, maximal protection against H3N2 was achieved at an HAI titer of 1:160 and an NT of 1:320, about twice as high a protective titer for H3N2 with a neutralization assay as with HAI. Considering LLOQ is the same for HAI with a neutralization assay, we chose 1:80 to define seroprotection, which is consistent with existing literature.^{1,2}

3.2.1.3. HAI (or H3N2-Neutralizing Antibody) Titer Seroconversion

HAI seroconversion from before SIIV (Visit 1) to 1 month after SIIV administration (Visit 2) will be defined for each participant as follow:

1. If the HAI titer is $< 1:10$ before SIIV administration, seroconversion is achieved if the postvaccination titer is $\geq 1:40$.
2. If the HAI titer is $\geq 1:10$ before SIIV administration, seroconversion is achieved if the fold rise in titer from before SIIV administration to after vaccination is ≥ 4 .

If a meaningful HAI is not obtainable, seroconversion from before SIIV (Visit 1) to 1 month after SIIV administration (Visit 2) for H3N2 NTs will be defined as below.

3. When the NT is $< 1:20$ before SIIV administration, seroconversion is achieved if the postvaccination NT is $\geq 1:80$.
4. When the NT is $\geq 1:20$ after SIIV administration, seroconversion is achieved if the fold rise in NT from before SIIV administration to after vaccination is ≥ 4 .

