9.3.4. Exploratory Endpoint(s)

Table 8. Exploratory Endpoint Analyses

Endpoint	Statistical Analysis Methods
Immunogenicity	
 CCI [REDACTED] For each HAI strain, counts and percentages of participants with seroprotection (defined as strain-specific HAI titers $\geq 1:40$) before vaccination and 1 month after vaccination with SIIV will be provided for each vaccine group, along with the associated Clopper-Pearson 95% CIs. Seroconversion is defined as an HAI titer $< 1:10$ before SIIV vaccination and an HAI titer $\geq 1:40$ 1 month after SIIV vaccination or an HAI titer $\geq 1:10$ before vaccination and a minimum 4-fold rise in HAI titer 1 month after SIIV vaccination. For each HAI strain, counts and percentages of participants with strain-specific HAI titer seroconversion 1 month after vaccination with SIIV, along with the associated Clopper-Pearson 95% CIs, will be provided for each vaccine group. Seroprotection and seroconversion for NTs will be defined in the SAP, and the analysis will be similar to HAI.

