5.3.2. Immunogenicity Data

Any assays above LLOQ are considered accurate and their quantitated values will be reported. Values below the LLOQ, or denoted as BLQ, will be set to $0.5 \times \text{LLOQ}$ for analysis.

For calculating a fold rise, $< \text{LLOQ}$ will be converted to $0.5 \times \text{LLOQ}$ for a numerator, and $< \text{LLOQ}$ will be converted to LLOQ for a denominator when only one of either the numerator or denominator is $< \text{LLOQ}$. If both the numerator and denominator are $< \text{LLOQ}$, then both will be converted in the same way.

The LLOQs for each assay will be included in the final released assay data.

Values for sera that are QNS, indeterminate results, or values recorded as “not done” will be set to “missing.” Additionally, any time point with no blood draws will not be included in the analysis. No imputation will be done for these missing values, as MCAR is assumed for immunogenicity data according to Scott and Hsu.⁶

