6.3.3. HAI (or H3N2-Neutralizing Antibody) Titer Seroconversion

Descriptive statistics, including the proportion (%) of participants who achieved seroconversion from Visit 1 to Visit 2, the numerator (n) and the denominator (N) used in the proportion calculation, and the 95% CI for percentage using the Clopper-Pearson method, will be presented for each vaccine group in the evaluable SIV immunogenicity population.

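### SAP 3.2.1.3 item 4 conditions H3N2 NT seroconversion on the titer after SIIV instead of before, so the two NT rules overlap and leave a gap

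*SAP*

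**What the plan says.** SAP Section 3.2.1.3 gives two pairs of rules.

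- **HAI, items 1 and 2.** Item 1 applies when the HAI titer before SIIV is below 1:10 and requires a postvaccination titer of at least 1:40. Item 2 applies when the titer is at least 1:10 "before SIIV administration, seroconversion is achieved if the fold rise in titer from before SIIV administration to after vaccination is" at least 4.
- **H3N2 NT, items 3 and 4**, used when a meaningful HAI result cannot be obtained. Item 3 applies when the NT is below 1:20 "before SIIV administration, seroconversion is achieved if the postvaccination NT is" at least 1:80. Item 4 applies when the NT is at least 1:20 "after SIIV administration, seroconversion is achieved if the fold rise in NT from before SIIV administration to after vaccination is" at least 4.

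Protocol Section 9.3.4 (Table 8) splits the HAI definition on the prevaccination titer. For neutralizing titers it gives no rule of its own: "Seroprotection and seroconversion for NTs will be defined in the SAP". The SAP text is therefore the only definition.

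The LLOQ matters here, and no value is stated. SAP Section 5.3.2 says "The LLOQs for each assay will be included in the final released assay data". SAP Section 3.2.1.2 says the two assays share it: "Considering LLOQ is the same for HAI with a neutralization assay, we chose 1:80 to define seroprotection".

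**The concern.** Items 1 to 3 all sort participants by their titer before SIIV. Item 4 alone sorts by the titer after. Items 3 and 4 therefore do not divide the participants between them: some meet both conditions and some meet neither, and nothing in SAP Sections 3.1.4.2, 5.3.2 or 6.3.3 sets an order of precedence.

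The rule can then be coded in more than one way with different results. If meeting either item is enough, the 1:80 requirement for low-baseline participants loses its force whenever the LLOQ is at or below 1:20, because everyone who passes item 3 also passes item 4. If participants under neither item are treated as unclassified, the denominator changes. What is at stake is the reported H3N2 seroconversion percentage in each group, should the NT fallback be used.

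**Working it through.** **Inputs from the documents.** The item 3 and item 4 conditions above. The fold-rise rule of SAP Sections 3.1.4.2 and 5.3.2: results below LLOQ become 0.5 × LLOQ, except that a prevaccination result below LLOQ becomes LLOQ when the postvaccination result is at or above LLOQ. The plan gives no figure to reproduce.

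**Reference rule.** The pattern of items 1 to 3: if pre < 1:20, success needs post ≥ 1:80; otherwise success needs a fold rise ≥ 4.

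**Step 1: overlap and gap.**

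| Before SIIV | After SIIV | Item 3 applies | Item 4 applies as written |
|---|---|---|---|
| < 1:20 | < 1:20 | yes | no |
| < 1:20 | ≥ 1:20 | yes | yes |
| ≥ 1:20 | ≥ 1:20 | no | yes |
| ≥ 1:20 | < 1:20 | no | no |

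**Step 2: direction of error.** Under the reference rule, a success with pre ≥ 1:20 has post ≥ 4 × 20 = 80, so item 4 as written also passes it. A success with pre < 1:20 has post ≥ 1:80 and passes item 3. No reference-rule seroconverter is lost, so letting either item suffice can only overstate.

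**Step 3: where the items conflict.** With LLOQ 1:10, 1:10 to 1:40 is a 4-fold rise: item 4 passes it, and item 3 fails it because 40 < 80. A prevaccination result below LLOQ is set to 10, so the same holds for it. With LLOQ 1:20, a low baseline is set to 20, a 4-fold rise means post ≥ 1:80, and the items agree.

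**Step 4: enumeration** of all pre/post pairs on 2-fold steps (below LLOQ, then LLOQ to 1:640):

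| LLOQ (assumed) | Pairs | Under both | In conflict | Under neither |
|---|---|---|---|---|
| 1:10 | 8 × 8 = 64 | 2 × 6 = 12 | 2 | 6 × 2 = 12 |
| 1:20 | 7 × 7 = 49 | 1 × 6 = 6 | 0 | 6 × 1 = 6 |

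**Step 5: which LLOQ is plausible.** HAI item 1 needs titers below 1:10. A result below LLOQ enters as 0.5 × LLOQ, and 0.5 × LLOQ < 10 requires LLOQ < 20. Since the SAP says the two assays share the LLOQ, a value below 1:20 is the one that lets the SAP's own HAI rule operate. This is an inference, not a stated value.

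**Step 6: illustrative size.** Bivariate log-normal titers, 400,000 draws per scenario, floored to 2-fold steps. All of the following are assumptions: baseline GMT 15, 25, 40, 80 or 160; fold rise 2.5, 4 or 6; log SD before/after of 1.4/1.7 or 1.0/1.3; correlation 0.5. Only 1.7 is a documented figure, namely the H3N2 SD in protocol Table 9, a maximum across age and vaccine groups.

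| LLOQ 1:10, either item suffices | GMT 15–40 | GMT 80–160 |
|---|---|---|
| SD 1.4/1.7 | +5.3 to +10.1 points | +0.9 to +2.9 points |
| SD 1.0/1.3 | +4.9 to +13.9 points | +0.3 to +1.9 points |

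- Example (GMT 15, 4-fold rise, SD 1.4/1.7): 36.0% by the reference rule against 45.8% if either item suffices, a difference of 9.8 points.
- Correlation 0.3 or 0.7 (GMT 15–40, SD 1.4/1.7): overstatement 4.5–9.8 or 5.5–11.0 points.
- LLOQ 1:20 or 1:40: overstatement 0.0 in all 30 scenarios each.
- Item 3 applied first, with uncovered participants counted as failures: 0.0 in every scenario.
- Share of overlapping participants with conflicting answers at LLOQ 1:10: 14–32%.
- Under neither item: 0.1–7.6% of participants at LLOQ 1:10 or 1:20 (up to 10.6% with correlation 0.3). At correlation 0.5, setting them to missing would raise the rate by 0.1–2.7 points.

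**The case against.** The strongest reply is that the meaning is obvious and little hangs on it. Item 3's condition is the natural complement of NT at or above 1:20 before SIIV, and the HAI pair follows that pattern in both documents. A careful programmer would query the word or read it as *before*.

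The gap is also mild. Everyone in it had a falling titer (fold rise 0.5 or less), so counting them as non-seroconverters is the sensible reading. SAP Section 5.3.2 sets only insufficient, indeterminate or not-done results to missing. The real conflict is confined to low baselines that rise at least 4-fold but stay below 1:80, and it disappears if the LLOQ is 1:20 or higher. The simulation rests mostly on inputs the documents do not supply.

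Much of this stands. Dropping gap participants from the denominator is a possible coding, not one the SAP directs, and the simulated sizes are only illustrative. But an obvious intention does not correct the text. This is the sole definition of the endpoint, its literal wording differs from the evident intention, and a silent correction in programming would be an undocumented departure from the SAP.

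**Conclusion.** The concern holds. Item 4 is wrong as written, and no other section corrects it. That items 3 and 4 overlap and leave a gap follows from their wording whenever titers below 1:20 can be recorded. That they give opposite answers depends on an LLOQ below 1:20, which the documents imply but do not state.

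The consequence is limited. The endpoint is exploratory, is reported descriptively per group with Clopper-Pearson intervals, and is used only if H3N2 HAI is not interpretable. The primary GMR comparisons, the fold-rise summaries, seroprotection and the power calculation are unaffected. It should be corrected, but it does not threaten the trial's main conclusions.

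**What to change.** In SAP Section 3.2.1.3, item 4, change *after* to *before* in the condition, so that the 4-fold rule applies to participants whose NT was at least 1:20 before SIIV. Items 3 and 4 then assign every participant with a baseline NT to exactly one rule, as items 1 and 2 do for HAI; repeating the enumeration with this change gives no pairs under both items and none under neither.

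The cost is one word in the SAP, made before programming. It needs no new data and changes no other endpoint.

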3.3. Baseline Variables

3.3.1. Baseline Definition

Day 1 is defined as the day of Vaccination 1. Measurements or samples collected prior to Vaccination 1 on Day 1 are considered the baseline data for the assessments.

3.3.2. Demographics, Smoking History, and Medical History

The demographic variables that will be collected include sex, race, racial designation, ethnicity, and date of birth. Age at the time of vaccination (in years) will be derived based on birthday. For example, if the vaccination date is 1 day before the participant's 86th birthday, the participant is 85 years old.

Medical history of clinical significance will be collected and categorized according to the current version (at the time of reporting) of MedDRA.

Tobacco use is also collected at baseline.

3.3.3. E-Diary Completion

An e-diary will be considered transmitted if any data for the local reactions and systemic events are present for any day. If all data are missing for all items (local reactions and systemic events) on the e-diary for all 7 days after vaccination, then the e-diary will be considered not transmitted. An e-diary will be considered transmitted for a given day if any data are present for that day.

3.3.4. Nonstudy Vaccines

Any nonstudy vaccinations received from 28 days prior to study enrollment through the conclusion of study participation will be collected.

Nonstudy vaccinations will be categorized according to the latest version (at the time of reporting) of the WHO Drug Dictionary.

3.4. Safety Endpoints

3.4.1. Adverse Events

AEs are classified into 1 of 3 tiers. Different analyses will be performed for different tiers (refer to [Section 6.6.1](#)).

- Tier 1 events: These are prespecified events of clinical importance and are maintained in a list in the product's safety review plan. As of this SAP finalization, no Tier 1 events have been identified for this vaccine.

- Tier 2 events: These are events that are not Tier 1 but are “relatively common.” A MedDRA PT is defined as a Tier 2 event if its incidence is at least 1% in any vaccine group.
- Tier 3 events: These are events that are neither Tier 1 nor Tier 2 events.

3.4.2. Vital Sign Data

The temperature collected at baseline will only be used to assess any potential protocol deviation for vaccination temporary delay. Therefore, it will not be included as a baseline variable.

4. ANALYSIS SETS (POPULATIONS FOR ANALYSIS)

Data for all participants will be assessed to determine if participants meet the criteria for inclusion in each analysis population prior to unblinding and releasing the database, and classifications will be documented per standard operating procedures.

Participant Analysis Set	Description
Enrolled	All participants who have a signed ICD.
Randomized population	All enrolled participants who are assigned a randomization number in the IRT system.
Safety population	All enrolled participants who receive the study intervention (RSVpreF, placebo, or SIIV).

Major protocol violations will be determined by clinical review. A major protocol violation is a protocol violation that, in the opinion of the sponsor’s study medical monitor, would materially affect assessment of immunogenicity or efficacy, eg, participant receipt of a prohibited vaccine or medication/treatment that might affect immune response or a medication error with suspected decrease in potency of the vaccine. The sponsor’s medical monitor will identify those participants with protocol violations before any analysis is carried out.

Defined Analysis Set	Description
Evaluable RSV immunogenicity population	All participants who meet the following criteria: 
 • Are eligible for the study; • Received the study interventions (RSVpreF, placebo, or SIIV) to which they were randomized at both Visit 1 and Visit 2; • Had the 1-month RSVpreF postvaccination blood collection 25 to 49 days after RSVpreF vaccination (25 days \leq Visit 2 - Visit 1 \leq 49 days for the coadministration group and 25 days \leq Visit 3 - Visit 2 \leq 49 days for the sequential-administration group); • Had no major protocol violations from randomization through the 1-month RSVpreF postvaccination blood draw; • Had at least 1 valid and determinate assay result (NT for RSV A or RSV B) 1 month after RSVpreF vaccination.
Evaluable SIIV immunogenicity population	All participants who meet the following criteria: 
 • Are eligible for the study; • Received the study interventions (RSVpreF, placebo, or SIIV) to which they were randomized in addition to SIIV at Visit 1; • Had the 1-month postvaccination blood collection 25 to 49 days after SIIV vaccination (25 days \leq Visit 2 - Visit 1 \leq 49 days); • Had no major protocol violations from randomization through the 1-month postvaccination blood draw; • Had at least 1 valid and determinate assay result (HAI titers or H3N2 NTs) 1 month after SIIV vaccination.
mITT immunogenicity population	All participants who were randomized and had at least 1 valid and determinate assay result at any time point after receiving study intervention (RSVpreF, placebo, or SIIV).

If a participant received study intervention not as randomized, the safety analysis set will be based on the vaccine group actually received and the immunogenicity analysis set will be based on the vaccine group as randomized.

5. GENERAL METHODOLOGY AND CONVENTIONS

5.1. Hypotheses and Decision Rules

5.1.1. Statistical Hypothesis for Primary RSV Immunogenicity

The primary immunogenicity objective on immune response elicited by RSVpreF will be evaluated by the following hypothesis for both RSV A and RSV B as measured by NT:

$$H_{01}: \ln(\mu_1) - \ln(\mu_2) \leq \ln(0.667)$$

where $\ln(0.667)$ corresponds to a 1.5-fold margin for noninferiority and $\ln(\mu_1)$ and $\ln(\mu_2)$ are the natural log of the geometric mean of NT at 1 month after vaccination with RSVpreF for the coadministration group (Visit 2) and the sequential-administration group (Visit 3), respectively. Noninferiority will be declared if the lower limit of the 2-sided 95% CI for the GMR (coadministration group to sequential-administration group) is >0.667 for both RSV A and RSV B NTs.

5.1.2. Statistical Hypothesis for Primary SIV Immunogenicity

The primary immunogenicity objective on immune response elicited by SIV will be evaluated by the following hypothesis for each strain included in SIV:

$$H_{02}: \ln(\mu_1) - \ln(\mu_2) \leq \ln(0.667)$$

where $\ln(0.667)$ corresponds to a 1.5-fold margin for noninferiority, and $\ln(\mu_1)$ and $\ln(\mu_2)$ are the natural log of the geometric mean of the strain-specific HAI titers (or H3N2-neutralizing antibody titers if interpretable H3N2-HAI titers cannot be obtained) 1 month after vaccination with SIV for the coadministration group and the sequential-administration group, respectively. Noninferiority will be declared for an influenza strain if the lower limit of the 2-sided 95% CI for the GMR (coadministration group to sequential-administration group) is >0.667 . The primary SIV immunogenicity objective of the study will be achieved if the noninferiority is met for each of the 4 influenza strains.

5.1.3. Multiplicity Adjustment

No multiplicity adjustment will be applied for this study. The primary objectives of noninferiority will be achieved only if the 1.5-fold equivalence criterion is met for each strain included in SIV and for both RSV A and RSV B antigens simultaneously. Each of the 6 statistical tests (4 from the SIV objective and 2 from the RSV objective) will use a 2-sided alpha level of 0.05.

5.2. General Methods

Unless otherwise stated, “CI” refers to a 2-sided CI in this document, either for 95% CI or Pocock-adjusted CI.

Descriptive statistics for binary variables are the proportion (%) and the numerator (n) and the denominator (N) used in the proportion calculation. The 95% CI for percentage, and for the difference in percentages, may also be presented, where appropriate.

Unless otherwise specified, descriptive statistics for continuous variables are n, mean, median, standard deviation, minimum, and maximum.

The subsections below describe the analysis for different types of endpoints.

